Gastrointestinal system comprises of more than 200 m² of mucosal surface. The immune system in gastrointestinal mucosa has been studied extensively until this day. The microflora or the microorganism in gastrointestinal system, also commonly known as the gut microbiome, is a part of the immunity system in gastrointestinal mucosa. Around 20% of malignancy are linked to microorganism. The gut microbiome is suspected to have a role in genetic and epigenetic changes that cause dysplasia, clonal expansion, tumor growth, and cancer. In addition, chronic

inflammation is also suspected to have a role in colorectal carcinogenesis. One of the chronic inflammation markers linked with carcinogenesis is NF- κ B.

Several studies showed that dysbiosis or imbalance of gut microbiome is linked with mucosal barrier damage, chronic inflammation and production of carcinogenic metabolite causing neoplasm. Thus far, the association between gut microbiome and colorectal cancer has provided an opportunity to develop new strategies in the screening method of colorectal cancer.

Non-invasive methods for colorectal cancer screening are currently being developed to replace colonoscopy. One of the screening methods is *fecal immunochemical test* (FIT) using fecal samples. This method has a sensitivity of 87.5% in detecting colorectal cancer cases. Another screening method uses blood sample to evaluate *carcinoembryonic antigen* (CEA) level in blood serum. An increase in CEA serum level of more than 5 ng/mL is found in 17-47% of colorectal patients and is associated with poor prognosis.

Research Objectives

General Objectives

To investigate the role of gut microbiome pattern and inflammation marker NF- κ B in colorectal cancer patients

Specific Objectives

1. To obtain data on gut microbiome pattern on young-onset colorectal cancer patients and colorectal cancer patients aged >50 years old.
2. To explore the role of inflammation marker NF- κ B on young-onset colorectal cancer patients and colorectal cancer patients aged >50 years old.
3. To obtain CEA values of young-onset colorectal cancer patients and colorectal cancer patients aged >50 years old.
4. To obtain data on gut microbiome which could be used as screening methods in patients suspected with colorectal cancer

Hypothesis

1. There are differences in gut microbiome pattern on young-onset colorectal cancer patients and colorectal cancer patients aged >50 years old compared to healthy individuals

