2. There are differences in NF- κ B on young-onset colorectal cancer patients and colorectal cancer patients aged >50 years old compared to healthy individuals
3. There are differences in CEA values on young-onset colorectal cancer patients and colorectal cancer patients aged >50 years old compared to healthy individuals

Research Benefits

For Researchers

Researchers will expand their knowledge on gut microbiome pattern in colorectal cancer patients.

For Institutions

This study will provide a contribution of science in national and international scale. The result of this study could be used as a guideline on utilizing gut microbiome data on colorectal cancer management.

For Communities

The result of this study is expected to improve the management of colorectal cancer as a screening method that would be applicable in daily clinical practice.

METHODOLOGY

Study Design

This is a cross-sectional study.

Time and Place

This study is conducted in [name] Hospital: Digestive Endoscopy Center, Department of Internal Medicine, Department of Clinical Pathology, Department of Anatomical Pathology, and Eijkman Institute of Molecular Biology from May 2019 to May 2022.

Population

Target Population

Patient suspected with colorectal cancer in Indonesia.

Accessible Population

Patients suspected with colorectal cancer who come to Digestive Endoscopy Center in [name] Hospital to conduct colonoscopy procedure and histopathological examination.

Subject Criteria

Inclusion Criteria

1. Age \geq 35 years old
2. Suspected with colorectal cancer and undergoing a colonoscopy procedure
3. No history of colorectal cancer treatment

Exclusion Criteria

1. Unwilling to provide fecal and blood sample
2. Incomplete colonoscopy procedure due to any reasons

Estimated Sample Size

Since this is a pilot study to obtain gut microbiome pattern on colorectal cancer patients, the number of samples is determined by the researchers: 100 subjects for neoplasm and 50 subjects for non-neoplasm (according to histopathology report).

Randomisation

The sampling will not be randomized. All patients suspected with colorectal cancer who come to Digestive Endoscopy Center in [name] Hospital to conduct colonoscopy procedure and histopathological examination who fulfilled the criteria will be recruited for this study and will undergo a series of examinations

Operational Definition

No.	Variable	Definition	Source	Scale

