1.	Patient suspected with colorectal cancer	Patient suspected with colorectal cancer by clinician based on clinical findings such as gastrointestinal bleeding, chronic constipation, chronic diarrhea, nonspecific abdominal pain, weight loss, palpable abdominal mass	Clinical judgement	Nominal
2.	Age	Patient's age (in years)	Medical record	
3.	Sex	Patient's sex	Medical record	Nominal
4.	Family history of colorectal cancer in a first-degree relative	First-degree relative: parents, sibling, children	Medical record and history taking	Nominal 1= No 2= Yes
5.	History of smoking	Past or current history of smoking	Medical record and history taking	Nominal 1= No 2= Yes
4.	FIT results	The result of Fecal immunochemical test (FIT)	Fecal immunochemical test (FIT)	Nominal 1= Negative 2= Positive
5.	Gut microbiome results	The result of gut microbiome examination	Next Generation Sequencing (NGS)	Nominal 1: Fusobacterium 2: Bacteroides 3. Lachnospiraceae

6.	NF- κ B results	The results of NF- κ B examination: positive if accumulated score ≥ 3	Examination with immune-histochemical method	Nominal 1= Negative 2= Positive
7.	CEA results	The results of Carcinoembryonic antigen (CEA) examination	Examination with ELISA method	Nominal 1= Negative 2= Positive
7	Histo-pathological results	The results of histopathological examination from biopsy samples are used as gold standard of colorectal cancer diagnosis	Medical record	Nominal 1 = Colorectal cancer 2 = Non-colorectal cancer

Ethical Approval

This study will be obtained ethical approval from the Ethics Committee of Faculty of Medicine, University of Indonesia.

Research Flow

Patients suspected with colorectal cancer who come to Digestive Endoscopy Center in [name] Hospital to conduct colonoscopy procedure and histopathological examination who fulfilled the criteria will be recruited for this study and will undergo a series of examinations. Each patient will be given an explanation of this study and will be asked his/her willingness to participate on this study by signing the informed consent form. Baseline characteristics data will be obtained from medical record. Before the colonoscopy procedure is conducted, each patient will undergo a score assessment, blood sampling, and fecal sampling.

1. Score Assessment

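### The sample-size groups, the histopathology code and the comparator in Hypotheses 1 to 3 do not match, and the study population contains no healthy group

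*Protocol*

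**What the plan says.** Three places in the protocol define groups.

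- **Estimated Sample Size** sets "100 subjects for neoplasm and 50 subjects for non-neoplasm (according to histopathology report". The same sentence calls the study a "pilot study to obtain gut microbiome pattern on colorectal cancer patients" and says that the researchers chose the number.
- **Operational Definition, histopathological results** is the only histopathology variable. It is the gold standard for the cancer diagnosis and is coded "Nominal 1 = Colorectal cancer 2 = Non-colorectal cancer".
- **Hypotheses 1 to 3** compare cancer patients in two age groups with a healthy comparator. The third reads: "There are differences in CEA values on young-onset colorectal cancer patients and colorectal cancer patients aged >50 years old compared to healthy individuals".

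On who is enrolled, an inclusion criterion is "Suspected with colorectal cancer and undergoing a colonoscopy procedure", and the definition of suspicion begins "Patient suspected with colorectal cancer by clinician based on clinical findings such as gastrointestinal bleeding". No criterion excludes benign or premalignant neoplasms. The protocol does not define neoplasm. Its own text uses the word in one other place, a background sentence on dysbiosis: "chronic inflammation and production of carcinogenic metabolite causing neoplasm".

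**The concern.** The three sets of labels should describe the same people, and nothing in the protocol links them. Two separate consequences follow.

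First, the hypotheses name a comparator that the recruitment rules cannot deliver. Patients referred for bleeding, weight loss or a palpable mass are not healthy individuals, even when histology shows no tumour. A difference found against them does not establish a difference from healthy people.

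Second, a patient with a benign or premalignant neoplasm has no settled place. Taken literally, the sample-size sentence counts that patient among the 100, while the code puts the same patient with the non-neoplastic patients. The 100 would then fix no number of cancers, although Objectives 1 to 3 describe cancer patients in two age groups. The only coded comparator for the hypotheses would also contain neoplasms.

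**Working it through.** **Step 1. Where each type of patient falls, with neoplasm read literally**

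| Patient | Sample-size group | Histopathology code | Place in Hypotheses 1 to 3 |
|---|---|---|---|
| Colorectal cancer | neoplasm (100) | 1 | cancer group |
| Other neoplasm | neoplasm (100) | 2 | none stated |
| Suspected cancer, non-neoplastic histology | non-neoplasm (50) | 2 | not healthy, so none stated |
| Healthy, no clinical suspicion | not eligible | none | the named comparator |

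The last row holds whatever neoplasm means: the named comparator is not enrolled. The second row is a problem only on the literal reading. If neoplasm means colorectal cancer, the 100 matches code 1 and the 50 matches code 2.

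**Step 2. The plan's own figure**

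The 100 and 50 (150 in total) come from no calculation. No alpha, power, effect size or precision is given, so there is nothing to reproduce.

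**Step 3. Illustration for the literal reading**

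Let *a* be the share of non-cancer neoplasms among the 100. The protocol does not give it; the values of 0, 10, 20 and 50% are assumptions.

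- Cancers = 100(1 − a).
- Coded non-cancer = 50 + 100a.
- Share of neoplasms among those coded non-cancer = 100a / (50 + 100a).
- 95% half-width for a proportion = 1.96 × √(p(1 − p)/n), where n is the number of cancers. For p, I use the 17 to 47% CEA positivity in the protocol's background.

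| a | Cancers | Coded non-cancer | Neoplasms among them | Half-width, p = 0.17 | Half-width, p = 0.47 |
|---|---|---|---|---|---|
| 0% | 100 | 50 | 0% | 7.4 points | 9.8 points |
| 10% | 90 | 60 | 17% | 7.8 | 10.3 |
| 20% | 80 | 70 | 29% | 8.2 | 10.9 |
| 50% | 50 | 100 | 50% | 10.4 | 13.8 |

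For example, at a = 20% and p = 0.47: 1.96 × √(0.47 × 0.53 / 80) = 0.109.

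The loss against 100 cancers is about 0.5 points or less at a 10% share, and about 3 to 4 points at 50% (10.4 − 7.4 = 3.0; 13.8 − 9.8 = 4.0). These figures pool both age groups. The age split is not given, and each age group's interval is wider.

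**Step 4. Precision of the comparator**

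The largest half-width for a comparator proportion (p = 0.5) is 13.9 points with 50 patients, 12.7 with 60, 11.7 with 70 and 9.8 with 100.

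**The case against.** The strongest reply is that neoplasm simply means cancer here. The sample-size sentence states its purpose as colorectal cancer patients, two groups by histopathology map naturally onto one two-level histopathology variable, and no objective or hypothesis names adenomas or other lesions as a study group. This stands as a plausible reading, and on it the sample-size mismatch has no numerical effect. It does not close the matter. The protocol says colorectal cancer in its objectives, hypotheses and definitions, and changes to an undefined, broader word only where it sets the numbers.

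A second reply is that the sizes above rest on assumed shares, and that a pilot with no stated target cannot miss one. That also stands. A reader might infer that the study is short of cancers or underpowered; the protocol does not support this, because it gives neither the share nor a power or precision goal. Choosing a pilot size without a power calculation is not a fault here.

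A third reply is that little is lost for good, since histology stays in the medical record and patients can be reclassified. That is true, and it keeps the severity down. It also makes the correction easy.

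A fourth is that the two-level code suits Objective 4, which seeks microbiome data "which could be used as screening methods in patients suspected with colorectal cancer". Agreed: for detecting cancer among suspected patients, other neoplasms belong with the non-cancers.

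None of these replies touches the healthy comparator, which is wrong on either meaning of neoplasm.

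**Conclusion.** The point holds, at minor to moderate severity. The firm part needs no assumption: Hypotheses 1 to 3 name a healthy comparator, and a population suspected of cancer on clinical findings does not contain one.

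The sample-size part is conditional. If neoplasm means colorectal cancer, it is inconsistent wording and nothing more. If it is literal, the 100 fixes no number of cancers, and non-cancer neoplasms enter the only coded comparator. How many is unknown; the 90, 80 and 50 cancers are illustrations of assumed shares.

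A reader might also infer that the hypothesis tests would be biased in a known direction. The documents do not support that: they give no marker levels for other neoplasms, and they state no analysis of neoplasm against non-neoplasm.

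**What to change.** 1. In Hypotheses 1 to 3, replace the healthy comparator by patients with suspected colorectal cancer and no neoplasm on histopathology, and limit the conclusions to that contrast.
2. Settle what neoplasm means.
   - If it means colorectal cancer, say so in the sample-size sentence, for both groups. While only the two-level code is kept, the comparator it can identify is patients without colorectal cancer; the wording in item 1 would have to match that, or other neoplasms be identified from the report.
   - If it is literal, record histopathology in three levels (colorectal cancer, other neoplasm, non-neoplastic) and state which levels fill the 100 and the 50. Report other neoplasms separately for Hypotheses 1 to 3, and keep them among the non-cancers for Objective 4.

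The cost is one table row, one sentence and the comparator wording. Histology already comes from the medical record, so no extra enrolment or procedure is needed if the 100 stays a number of neoplasms.

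There are two downsides with three levels. The number of cancers may be below 100 and is still not fixed; the protocol would then say openly that the 100 counts neoplasms. Hypotheses 1 to 3 would use 50 comparators instead of all non-cancers (50 to 100 under the assumed shares), with a largest half-width of 13.9 points instead of 13.9 down to 9.8.

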Asia Pacific Colorectal Screening (APCS) is a validated tool to predict the risk of colorectal cancer in asymptomatic Asian population. The scoring system comprises of three categories: low risk (score 0-1), moderate risk (score 2-3) and high risk (score 4-7). Patients with moderate and high risk will undergo further examinations

Table. Asia Pacific Colorectal Screening (APCS).

Risk Factor	Criteria	Score
Age (in years)	< 50	0
	50 – 69	2
	≥ 70	3
Sex	Female	0
	Male	1
Family history of colorectal cancer in a first-degree relative	Absent	0
	Present	2
History of smoking	Never	0
	Current or past	1

2. Blood Sampling

[figure not shown]
Blood samples will be taken before colonoscopy procedure to evaluate the level of serum CEA by ELISA method and to evaluate the presence of NF- κ B by immunohistochemical method.

- a. Carcinoembryonic antigen (CEA) is a well-known marker for colorectal cancer. A pre-treatment serum CEA level of ≥ 5 ng/mL is associated with poor prognosis in colorectal cancer patients.
- b. NF- κ B is a chronic inflammation marker found in colorectal cancer patients

3. Fecal Sampling

Fecal samples will be taken before colonoscopy procedure to be tested for FIT and to evaluate the gut microbiome.

- a. Fecal immunochemical test (FIT) is a recommended screening method for colorectal cancer. Detection of hemoglobin over a certain level in fecal samples indicated a positive FIT. Patients with positive FIT will undergo further examinations.
- b. Gut microbiome examination will be conducted with next generation sequencing (NGS) method.

Blood samples and fecal samples will be tested in Department of Clinical Pathology [name] Hospital, while gut microbiome will be evaluated in Eijkman Institute of Molecular Biology. Colonoscopy procedure will be conducted in Digestive Endoscopy Center [name] Hospital. Histopathological examination be conducted in Department of Anatomical Pathology [name] Hospital. The results of colonoscopy procedures and histopathology report will be obtained from medical record.

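### The reference diagnosis is biopsy histology with two codes and no provision for a resection specimen or a non-diagnostic biopsy, so a cancer shown only on resection is literally coded as non-cancer

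*Protocol*

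**What the plan says.** The last row of the protocol's Operational Definition table sets the reference standard: "The results of histopathological examination from biopsy samples are used as gold standard of colorectal cancer diagnosis". The source is the medical record and the scale is "1 = Colorectal cancer 2 = Non-colorectal cancer".

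Other sections bear on how this row works:

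- Research Flow: "The results of colonoscopy procedures and histopathology report will be obtained from medical record". No specimen type and no cut-off date is given.
- Estimated Sample Size: the groups are "100 subjects for neoplasm and 50 subjects for non-neoplasm (according to histopathology report"). This splits on neoplasm, not on cancer.
- Hypothesis: the comparison is of young-onset patients and "colorectal cancer patients aged >50 years old compared to healthy individuals".
- Inclusion Criteria: every subject is "Suspected with colorectal cancer and undergoing a colonoscopy procedure".
- Exclusion Criteria: the only exclusion that touches the diagnostic work-up is "Incomplete colonoscopy procedure due to any reasons".
- Study Design: "This is a cross-sectional study". No follow-up is described.

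The protocol does not mention a resection specimen, an inadequate or indeterminate biopsy, or a rule for choosing among several pathology reports.

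**The concern.** Every subject enters under clinical suspicion of cancer, and a palpable mass is among the listed findings. A biopsy without invasive tumour is weaker evidence of no cancer here than in healthy volunteers. Suppose a subject has a complete colonoscopy and a visible mass, the biopsy shows only necrosis or inflammation, and the resection specimen later shows cancer. No exclusion removes this subject, there is no third code, and the definition names biopsy samples only. The literal code is 2.

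The error goes in one direction, placing true cancers among the comparators. If those cancers carry the markers about as often as detected ones, the microbiome, NF-κB and CEA differences shrink. A marker-positive missed cancer also counts as a false positive, so specificity looks lower than it is. That matters for the fourth specific objective, which looks for microbiome data usable in screening.

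**Working it through.** The protocol's sample size (100 + 50 = 150) was chosen by the researchers, so there is no power calculation to reproduce. What follows is a sensitivity illustration.

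**Inputs from the protocol.** Total 150, planned as 100 neoplasm and 50 non-neoplasm. Serum CEA is raised in 17–47% of colorectal cancer patients (background section), midpoint (17 + 47)/2 = 32%.

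**Assumed inputs (not in the protocol).** Share m of true cancers that the biopsy misses: 5% to 15%. CEA positivity in true non-cancers: 10%. Missed cancers are CEA-positive as often as detected ones (32%). Two-sided alpha 5%.

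**Formulas.** With T subjects coded cancer and C = 150 − T coded non-cancer:

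- missed cancers M = T·m/(1 − m)
- contamination c = M/C
- observed comparator positivity p0' = (1 − c)·10% + c·32%
- observed difference = 22·(1 − c) points
- observed specificity = 100% − p0'
- power = Φ[(d − 1.96·SE0)/SE1], where d is the observed difference, SE0 its pooled and SE1 its unpooled standard error

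**Scenario A, worst case: T = 100, C = 50.** Every planned neoplasm is a biopsy-proven cancer, and every missed cancer lands among the 50.

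- m = 5%: M = 100 × 0.05/0.95 = 5.3; c = 5.3/50 = 10.5%
- m = 15%: M = 100 × 0.15/0.85 = 17.6; c = 17.6/50 = 35.3%

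**Scenario B: T = 50, C = 100.** Half the planned neoplasms are cancers, and the Operational Definition's cancer/non-cancer split is used.

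- m = 5%: M = 50 × 0.05/0.95 = 2.6; c = 2.6/100 = 2.6%
- m = 15%: M = 50 × 0.15/0.85 = 8.8; c = 8.8/100 = 8.8%

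**Effect on the CEA illustration:**

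| Scenario | m | Contamination | Difference (points) | Specificity | Power |
|---|---|---|---|---|---|
| A | 0 | 0 | 22.0 | 90.0% | 88% |
| A | 5% | 10.5% | 19.7 | 87.7% | 77% |
| A | 15% | 35.3% | 14.2 | 82.2% | 45% |
| B | 0 | 0 | 22.0 | 90.0% | 90% |
| B | 5% | 2.6% | 21.4 | 89.4% | 88% |
| B | 15% | 8.8% | 20.1 | 88.1% | 82% |

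One figure needs no miss rate: in a comparator of 50, each missed cancer is 1/50 = 2% contamination.

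**Which split applies matters.** Under the Estimated Sample Size split, a biopsy showing dysplasia or adenoma without invasion is still neoplasm and does not enter the 50. Only a biopsy with no neoplastic tissue would. Under the Operational Definition code, the dysplasia-only biopsy is coded 2. Scenario A puts all missed cancers into the smaller group, and so overstates the effect unless none of the missed biopsies shows neoplasia.

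**The case against.** A reader might infer that the protocol freezes the first biopsy and forbids any later update, so that even a positive repeat biopsy would be ignored. The text does not support this. The definition speaks of biopsy samples in the plural, taken from the medical record, with no cut-off; a repeat biopsy is covered. The sample-size and Research Flow sections speak more broadly of the histopathology report. A cross-sectional design does not bar reading a later report. The protocol is silent on updating and does not prohibit it. What stands is narrower: the definition itself leaves out a resection-only diagnosis and gives no code for a non-diagnostic biopsy.

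A reader might also take 11% to 35% as the expected contamination. It is a worst case on an assumed rate. The relevant rate is cancers still missed after all biopsies in the record, which cannot exceed the rate for a first biopsy. If missed cancers carry the markers less often than detected ones, the shrinkage is smaller again.

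Two further objections have weight. Biopsy histology as a reference standard is not an error in itself, and this is a pilot. And dropping visible masses with non-diagnostic histology from the comparator would remove the hardest non-cases and could inflate specificity. The fix should therefore not simply exclude them.

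It could be said that choosing the final report belongs in an analysis plan. But the protocol itself fixes the specimen and the scale of the reference standard, and the group quotas are filled from histopathology, so the correction belongs in the same table.

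**Conclusion.** The point holds in a limited form. The definition names biopsy histology only, with two codes, and so places a cancer shown only on resection in the comparator. The expected effect is bias toward zero in the marker differences and understated specificity, provided that missed cancers resemble detected ones in their markers.

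The size is unknown. On assumed miss rates of 5% to 15%, contamination is about 3% to 9% under a 50/100 cancer/non-cancer split, which costs the CEA illustration 0.6 to 1.9 of 22 points. The 11% to 35% range applies only if every missed cancer falls among 50 comparators. No new sample size follows from this. It is a worthwhile, inexpensive improvement and does not invalidate the design. It also depends on a choice the protocol leaves open, namely whether the comparator is healthy, non-neoplasm or non-cancer.

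**What to change.** In the histopathology row of the Operational Definition table:

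1. Define the reference result as the final pathology in the medical record, from any biopsy, repeat biopsy or resection specimen, within a stated window after colonoscopy. The window should preferably have the same length for every subject. Sampling runs from month 4 of year 1 to month 3 of year 2, so a single calendar cut-off would give the first recruits about a year longer than the last for a cancer to come to light.
2. Use one group definition throughout, consistent with the neoplasm/non-neoplasm split in Estimated Sample Size, and say where a dysplasia- or adenoma-only result falls.
3. Add an indeterminate flag for a visible mass with non-diagnostic histology and no later pathology. Report results with and without these subjects.

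The cost is a later look at records already in use and a few subjects flagged indeterminate. No new procedure is needed and patient management does not change. The Timeline has room: analysis starts in month 4 of year 2 and runs to month 3 of year 3.
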